8.2.7. Definition of Dose Limiting Toxicity (DLT)

National Cancer Institute CTCAE Version 4.03 are used as a guide for the grading of severity of adverse events (except as otherwise specified). Dose-limiting toxicities are described below:

- A non-hematologic AE that is clearly not related to disease progression, medical procedure or intercurrent illness and that commences within 28 days of first CC-122 dose and is \geq Grade 3 EXCEPT for:
 - Alopecia
 - Grade 3 rash of the acneiform or maculopapular type of not more than 4 days durations (with optimal medical management)
 - Grade 3 diarrhea or vomiting lasting less than 72 hours (with optimal medical management)
 - Grade 3 diarrhea requiring hospitalization and Grade 3 nausea or vomiting that required tube feeding, total parenteral nutrition, or hospitalization will be considered DLTs
- Tumor lysis syndrome (TLS), unless TLS does not progress to Grade 2 and resolves in less than 7 days with medical management
- \geq Grade 3 tumor flare reaction (per NCI CTC AE Version 3.0)
- Laboratory abnormality that is clearly not related to disease progression, medical procedure or intercurrent illness and that commences within 28 days of first dose of CC-122 and is \geq Grade 3 (unless otherwise specified below)
- Hematological toxicities as follows (grading as per IWCLL criteria):
 - Any febrile neutropenia
 - Grade 4 neutropenia lasting > 7 days
 - Any Grade 3 or 4 thrombocytopenia with clinically significant bleeding
 - Any cytopenia that requires dose reduction during the DLT evaluation period
- Grade 4 liver function tests or Grade 3 ALT with Grade 2 or higher bilirubin will be considered a DLT irrespective of underlying attribution
- Any AE assessed as clearly not related to disease progression, medical procedure or intercurrent illness and necessitating dose-level reduction during the DLT evaluation period.

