8.2.9.2. Dose Modification Guidelines

Any IP-related toxicity meeting the definition of DLT will require dose reduction or interruption. The criteria for dose reduction are listed in [Table 14](#), should be used for dose modifications.

Chronic Grade 2 toxicity (other than specified below) may warrant dose reduction or interruption of one or both IP. Such cases should be discussed with the sponsor's medical monitor before changes are made.

Dose modification decisions for patients with cytopenia (below the lower limit of the normal range) at **baseline** will be based on the IWCLL guideline ([Table 13](#)). For patients with a normal neutrophil count, platelet count and/or hemoglobin value at baseline, the NCI CTCAE (version 4.03) will be used.

Any dose modifications must be recorded on the respective Study Drug Record eCRF.

Table 14: Dose Reduction Guidelines

Adverse Event	Grade	Action	Agent to be considered for interruption/reduction (in descending order)
Thrombocytopenia	≥ Grade 3	
• Hold all IP• Follow CBC at least every 7 days• If thrombocytopenia resolves to ≤ Grade 2, restart IP and reduce CC-122 to the next lower dose level. Ibrutinib may be restarted after thrombocytopenia resolves to ≤ Grade 1 or baseline at original dose after the 1st occurrence, and reduce by one dose level at each subsequent recurrence with a maximum of 2 dose reductions allowed. A 4th recurrence requires permanent discontinuation of ibrutinib.• Obinutuzumab should be restarted at the full dose after thrombocytopenia resolves to ≤ Grade 2, no dose reduction is allowed.	
• CC-122• Ibrutinib/obinutuzumab

Table 14: Dose Reduction Guidelines (Continued)

Adverse Event	Grade	Action	Agent to be considered for interruption/reduction (in descending order)

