Up to approximately 20 subjects will be enrolled to Arm A to assess an intrasubject dose escalation schedule for CC-122.

If > 20% (e.g., >4 of 20) of subjects meet the criteria for DLT within 28 days of initial escalation to a dose level, no further intrasubject dose escalation to that dose level will be permitted.

Early DLT Evaluation for Fixed-Doses Cohorts in Arms B and C:

An initial 3 subjects will be enrolled to each of the fixed-doses escalation cohorts in Arms B and C. A dose level will be considered tolerable if 0 of 3 treated subjects experiences a DLT during the DLT evaluation period of each respective group. If 1 of 3 subjects experiences a DLT, 3 additional subjects will be enrolled to that dose level. A dose will be considered the NTD when ≥ 2 out of 6 evaluable subjects in a cohort experience a DLT. If DLTs are observed in ≥ 2 out of 6 evaluable subjects at the first dose level, a lower dose combination may be explored after review of safety data by the SRC (see Protocol Section 8.2.1).

After full enrolment and completion of the DLT evaluation period of each dose level, the number and type of DLTs and AEs occurring during the DLT evaluation period will be evaluated. A dose level will be considered tolerated after discussion of these data by the SRC. Subsequent dose cohorts will only be authorized to open for enrolment following a consensus by the SRC. Subjects enrolled in lower CC-122 fixed-dose cohorts will be allowed to escalate immediately to the next higher CC-122 dose level upon SRC approval of the subsequent CC-122 dose. For example, if the SRC has declared the 1.0 mg dose level tolerable and confirmed the opening of the 1.5 or 2.0 mg dose level, the subjects in the lower combination, ie, 0.5 mg CC-122 dose level may escalate to 1.0 mg.

The MTD is defined as the highest dose level below the NTD with 0 or 1 of 6 DLT evaluable subjects experiencing a DLT during the specified DLT evaluation period. If only 3 subjects have been enrolled at the last dose level below the NTD, 3 additional subjects will be enrolled. A dose level will be declared the MTD when at least 6 subjects have been enrolled and less than 2 subjects have experienced a DLT at that dose level.

An intermediate dose (i.e. one between the NTD and the last dose level before the NTD) or additional subjects within any dose cohort may be required to determine the MTD and RP2D more precisely.

Monitoring for Late Toxicities during the Dose Escalation Phase:

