5.2.2. Dose Limiting Toxicity (DLT) Evaluable Population

DLT Evaluable population –

- Arm A: is defined as all subjects who completed at least one cycle of treatment and did not miss more than 5 days of CC-122 dosing during the first cycle are to be considered evaluable for DLT, unless the missed doses were due to IP related AE(s) or the cycle was not completed due to a DLT, in which case they remain evaluable for DLT.
- Arm B: is defined as all subjects who completed at least one cycle of CC-122 (Cycle 2 Day 1 through Cycle 2 Day 28) and did not miss more than 5 days of CC-122 treatment are to be considered evaluable for DLT, unless the missed doses were due to IP related AE(s) or the cycle was not completed due to a DLT, in which case they remain evaluable for DLT.
- Arm C: is defined as all subjects who completed at least one cycle of CC-122 (Cycle 1 Day 9 through Cycle 2 Day 8) and did not miss more than 5 days of CC-122 treatment are to be considered evaluable for DLT, unless the missed doses were due to IP related AE(s) or the cycle was not completed due to a DLT, in which case they remain evaluable for DLT.

Subjects will be summarized under the starting treatment arm and starting dose of CC-122 they initially received.

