8.4. Dose Reduction/Interruptions

Dose reduction is defined as a decrease in dose (non-zero) relative to the immediately previous dose (or assigned dose if the first dose). Dose interruption occurs if the record of actual administered dose is zero except as required by the protocol (i.e. for CC-122 the 2 out of 7 days when the subject does not receive CC-122 drug). If an interruption happens at the start of a cycle and causes the cycle to be postponed, it is also called dose delay. Consecutive zeros are counted as one interruption. The reductions will be derived from the data collected.

Dose modifications are permitted in any cycle, including Cycle 1 and the DLT evaluation period:

- Dose reductions that occur during the DLT evaluation period will constitute a DLT, but subjects will be allowed to continue on IP at a reduced dose.

- Dose reductions are allowed for CC-122 and ibrutinib. No dose reductions are allowed for obinutuzumab, but treatment may be discontinued at the discretion of the investigator for severe infusion or allergic reactions.

Dose reduction, where applicable, and interruption will be summarized separately by dose cohort and overall for each arm. Summaries include the following:

- Number of subjects with dose reductions or interruptions;
- Number of dose reductions/interruptions due to AE;
- Descriptive statistics of time to the first dose reduction or interruption (from the first dose) due to an AE for those who have at least one dose reduction or interruption due to an AE;
- Descriptive statistics of total days of dose reduction or interruption due to an AE for those who have at least one dose reduction or interruption of CC-122 and Ibrutinib due to an AE;
- Number and percentage of subjects who have at least two dose reductions or interruptions.

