11.1.2. Dose-limiting Toxicities (DLTs)

DLT is defined as a treatment-related AE(s) occurring in Cycle 1 (the first 28 days of treatment with CC-122 and combination therapy) that meets one of the criteria defined in the Protocol Section 8.2.7. Subjects will be observed for early DLTs for 28 days following the initiation of CC-122 (for Arm A, Cycle 1 day 1 through Cycle 1 Day 28; for Arm C, Cycle 1 day 9 through Cycle 2 day 8, and for Arm B, Cycle 2 Day 1 through Cycle 2 Day 28) (DLT evaluation period).

A summary table of DLTs during DLT evaluation period will be presented by dose cohort and treatment arm including number and percentage of subjects having a DLT. The percentage of subjects having a DLT is based on the number of subjects who are CC-122 evaluable for DLT Evaluable population. Listing of AEs which meet dose limiting toxicity will be provided.

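### The SAP counts only treatment-related DLTs, but no DLT criterion in Protocol 8.2.7 requires relatedness, so the primary-endpoint DLT table can understate protocol-defined DLTs

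*SAP*

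**What the plan says.** SAP 11.1.2 states: "DLT is defined as a treatment-related AE(s) occurring in Cycle 1 (the first 28 days of treatment with CC-122 and combination therapy"), and the same sentence adds that the event must meet one of the criteria in Protocol 8.2.7. Both conditions must hold. The section then plans a table of the number and percentage of subjects with a DLT, by dose cohort and arm, on the DLT Evaluable population, together with a listing.

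Protocol 8.2.7 defines DLTs without a relatedness condition. A typical criterion begins "A non-hematologic AE that is clearly not related to disease progression, medical procedure or intercurrent illness". The liver criterion reads "Grade 4 liver function tests or Grade 3 ALT with Grade 2 or higher bilirubin will be considered a DLT irrespective of underlying attribution". One hematological sub-criterion is "Any cytopenia that requires dose reduction during the DLT evaluation period".

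Two other SAP sections bear on the point. SAP 8.4 says "Dose reductions that occur during the DLT evaluation period will constitute a DLT". SAP 5.2.2 keeps a subject with an incomplete window evaluable if the missed doses were due to an IP-related AE or if "the cycle was not completed due to a DLT, in which case they remain evaluable for DLT".

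Protocol 3.1 includes DLTs in the primary endpoint.

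**The concern.** The SAP narrows a protocol definition that feeds the primary endpoint, and Section 15, which lists departures from the protocol's statistical section, does not mention it. An added condition can only remove events, so any error runs one way, towards fewer reported DLTs.

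In cohorts of three to six subjects, one event separates a tolerated dose level from an NTD. A table built on the narrower definition can therefore disagree with the way a cohort reads under the protocol's own criteria. Nothing in the planned output would show the reader why.

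**Working it through.** The documents give no figure to reproduce. The check compares the definitions and then does simple arithmetic at the protocol's cohort size.

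**Step 1. The seven top-level criteria of Protocol 8.2.7 against the SAP condition.**

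| Criterion | Cause test in 8.2.7 | Effect of the SAP condition |
|---|---|---|
| Non-hematologic AE, Grade 3 or higher | Clearly not due to progression, procedure or intercurrent illness | Narrows |
| Laboratory abnormality, Grade 3 or higher | Same | Narrows |
| AE necessitating dose-level reduction | Same | Narrows |
| Tumor lysis syndrome | None | Adds a filter |
| Tumor flare, Grade 3 or higher | None | Adds a filter |
| Hematological toxicities (four sub-criteria) | None | Adds a filter |
| Liver tests | Attribution expressly disregarded | Direct contradiction |

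Count: 3 with a limited cause test, 3 with none, 1 that disregards attribution; 3 + 3 + 1 = 7. Criteria requiring relatedness: 0 of 7. Criteria without any cause test: 3 + 1 = 4 of 7.

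**Step 2. The three narrowed criteria.** Ruling out progression, procedure and intercurrent illness is not the same as suspecting the drug. Under Protocol 11.2.3 an event is also classed as not suspected when other medications sufficiently explain it. Such an event meets 8.2.7 and fails SAP 11.1.2.

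**Step 3. How the protocol treats relatedness elsewhere.** Protocol 8.2.9.2 says "Any IP-related toxicity meeting the definition of DLT will require dose reduction or interruption". The qualifier would be redundant if every DLT were related by definition. Protocol 10.7 plans the DLT summary without a relatedness limit and names IP-related events as a separate tabulation.

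**Step 4. Numerator.** Take a cohort of 6 with 2 events meeting 8.2.7, one of them judged unrelated.

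- Protocol definition: 2/6 = 33.3%.
- SAP definition, subject still evaluable: (2 − 1)/6 = 1/6 = 16.7%.

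**Step 5. Denominator.** Suppose the subject with the unrelated event also stopped early because of it. Under the SAP's definition the missed doses were not due to an IP-related AE and the stop was not due to a DLT. Neither exception in SAP 5.2.2 applies, and the subject leaves the population: (2 − 1)/(6 − 1) = 1/5 = 20.0%.

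**Step 6. Illustration under assumed values.** Let p be the rate of 8.2.7 DLTs and u the share judged unrelated; neither comes from the documents. The tabulated rate is r = p(1 − u). The chance that a cohort would read as passing 3+3 on the tabulated events (0/3, or 1/3 then 0/3) is (1 − r)³ + 3r(1 − r)² × (1 − r)³.

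| p | u | r | Chance of reading as a pass |
|---|---|---|---|
| 0.30 | 0 | 0.30 | 0.494 |
| 0.30 | 10% | 0.27 | 0.557 |
| 0.30 | 20% | 0.24 | 0.622 |
| 0.30 | 50% | 0.15 | 0.814 |

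Between u = 0 and u = 50%, the chance goes from 0.709 to 0.906 at p = 0.20 and from 0.309 to 0.709 at p = 0.40. These figures show how sensitive the reading is; they do not describe dose decisions actually taken.

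**The case against.** The strongest reply is that the protocol itself is ambiguous. Protocol 8.2.5 bases the NTD on an IP-related DLT, so the SAP wording may simply follow that section. This stands as a likely origin of the wording and as a conflict inside the protocol, because Protocol 4.1 and 8.2.6 say only DLT. It does not rescue SAP 11.1.2: 8.2.5 qualifies which DLTs count towards the NTD, not what a DLT is.

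The gap may also be small. SAP 5.1 defines study treatment as any of CC-122, ibrutinib or obinutuzumab, so attribution to any one of them would pass the filter. Few tumor lysis, tumor flare or cytopenia events may be judged unrelated to all of them. That limits the likely number of events, but not the contradiction on liver tests.

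The denominator effect depends on reading the DLT exception in SAP 5.2.2 with the SAP's own definition; that section does not refer to 11.1.2. Subjects not evaluable for DLT who withdraw for reasons other than DLT are also replaced (Protocol 10.3, SAP 4.4). If the narrower definition had been used during the study as well, the cohort would have returned to six. The 1/5 case therefore assumes that the cohort was run on 8.2.7 and tabulated on 11.1.2.

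The events are not hidden. SAP 11.1.1 plans unfiltered tables of febrile neutropenia, tumor flare and tumor lysis by cycle of onset, and of TEAEs leading to dose reduction or discontinuation by CC-122 cycle. None of these labels an event as a DLT.

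Finally, SAP 4.1 speaks of subjects "out of 6 evaluable subjects in a cohort experience a DLT" with no qualifier. That is ordinary use of a defined term, and nothing here rests on it. The SAP 8.4 sentence carries more weight, because it says outright what constitutes a DLT, although it repeats Protocol 8.2.9.

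**Conclusion.** The concern holds and should be fixed. As written, SAP 11.1.2 can drop events that Protocol 8.2.7 counts as DLTs from a primary-endpoint table, and the change is undeclared. For the liver criterion no reading satisfies both documents.

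The size is one subject at a time: 33.3% becomes 16.7%, or 20.0% under the conditions in Step 5. The total effect cannot be derived from the documents and may be nil. SAP 11.1.2 does not say how treatment-related is derived; the suspected/not suspected field of Protocol 11.2.3 is assumed here.

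The consequence is limited to reporting. The SRC decides tolerability and the recommended dose (Protocol 4.1), enrollment has closed, and Phase 2 will not proceed.

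**What to change.** - In SAP 11.1.2, define the tabulated DLT as any event meeting Protocol 8.2.7 within the arm-specific 28-day window already given there.
- State in SAP 5.2.2 that the DLT exception uses the same definition.
- Show investigator attribution as a second row of the table or a column of the DLT listing.
- If the relatedness filter is intended, declare and justify it in SAP Section 15, name the field that derives it, and also show the unfiltered count.
- Reconcile Protocol 8.2.5 with 4.1, 8.2.6 and 8.2.7 so that the NTD and the maximum tolerated dose (MTD) count the same events. Which wording should prevail is for the sponsor to settle.

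The SAP cost is small: a sentence in 11.1.2 with the matching cross-reference in 5.2.2, one derived flag, and one row or listing column. The reported DLT rate may be slightly less favourable.

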11.1.3. Adverse Events Subgroup Analysis

As per request of German EC, additional summary tables by SOC and PT will be provided for TEAE and SAE, grouping subjects by gender or age class (≤ 70 years, > 70 years).

11.2. Clinical Laboratory Evaluations

Clinical laboratory tests include:

- Amylase, Lipase, fasting lipid profile, Creatine Kinase, Thyroid-Stimulating Hormone (TSH), Free T4 (fT4), Immunoglobulins (IgG, IgM and IgA only), T-cell subsets.
- Complete Blood Count (CBC): HGB, Hematocrit, Red Blood Cell (RBC) count with indices, WBC count with absolute differential and Platelet count.
- Serum chemistry: Albumin, Total Protein, Bicarbonate, Calcium, Phosphorus, Serum Creatinine, Serum Urea/Blood Urea Nitrogen (BUN), Glucose (fasting), Potassium, Sodium, Magnesium, Chloride, Total Bilirubin, ALP, AST/SGOT, ALT/SGPT, and LDH, Uric Acid, Troponin T and B-type Natriuretic Peptide (BNP).
- Beta-2 Microglobulin
- C-Reactive Protein.
- Direct Antiglobulin test (local laboratory only).
- Coagulation tests: Prothrombin Time, INR and, PTT.
- Urinalysis: dipstick, with microscopy in event of positive (1+ or greater) blood or protein and 24-hour collection for creatinine clearance and protein quantification in the event of 2+ or greater protein.
- Virus Serology: Hepatitis B surface Antigen (HBsAg), Hepatitis B core antibody (anti-HBc), and Hepatitis C Virus (HCV) RNA.

Clinical laboratory values will be graded, for applicable tests, according to NCI CTCAE version 4.03 or to IWCLL guidelines for the diagnosis and treatment of CLL ([Section 17.8](#)). The value from selected laboratory tests and the change from baseline value will be summarized using descriptive statistics by dose cohort/treatment arm for the timepoints when baseline, maximum or minimum values were observed.

Bidirectional shift tables (low and high) demonstrating the change of NCI CTCAE grades from baseline to worst post-baseline during the treatment period will also be presented by, treatment arm and dose cohort. In addition, frequency count of the worst post-baseline NCI CTCAE grades (low, high) during the treatment period will also be presented by treatment arm and dose cohort.

Summaries of laboratory values by treatment arm, dose cohort, cycle and maximum NCI CTCAE grade will be provided.

Listings of clinical laboratory data, including cardiac laboratory data, with NCI CTCAE grades (if applicable) and abnormal flags (low or high) will be provided.

For some key laboratory tests (HGB, Platelet, ANC,), spaghetti plots for each arm separately will be presented to show the pattern of the laboratory test percent change from baseline over time using the Safety population in dose escalation phase. All non-missing laboratory test values including assessments at scheduled, unscheduled, or EoT visits, will be presented. The X axis will be ticked at the study days, and the Y axis will be the percent change from baseline values. Values for the EoT visit will be included in spaghetti plots but will be displayed for the nominal visit equal to or immediately after the EoT visit.

11.3. Vital Sign Measurements

Vital sign values and change from baseline will be summarized using descriptive statistics by treatment arm, dose cohort, and overall for the timepoints when baseline, maximum or minimum values were observed.

Shift tables demonstrating the changes (low/normal/high) from baseline to worst post-baseline value will be displayed in cross-tabulations by arm and dose cohort for vital sign measurements. Normal ranges given in [Table 6](#) will be used to determine the categories of low, normal, and high.

Data collected for vital sign measurements will be listed.

Table 6: Normal Ranges of Vital Sign Measurements

Test	Normal Range (Unit)
Diastolic Blood Pressure (DBP)	[60, 90] (mmHg)
Systolic Blood Pressure (SBP)	[100, 140] (mmHg)
Pulse	[60, 100] (bpm)
Temperature	[35, 38] (°C)
Respiration	[12, 20] (BPM)

11.4. Electrocardiograms (ECG)

Shift from baseline to worst post-baseline in the overall ECG interpretation ('Normal' 'Abnormal, not clinically significant' and 'Abnormal, clinically significant' will be displayed in cross-tabulations by treatment arm and dose cohort.

A listing of ECG by treatment and dose cohort will be provided.

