6.1.5. Cardiac Laboratory Testing

Subjects will undergo laboratory monitoring of plasma troponin-T and B-type natriuretic peptide (BNP) to evaluate for potential early evidence of cardiac toxicity. Testing will be performed at Screening, weekly during the first cycle of CC-122 treatment and for the first cycle of each dose escalation (Days 1, 8, 15, and 22), Day 1 of each subsequent cycle, and at the EOT visit. A significant elevation of troponin-T is defined as a value greater than the upper limit of normal (ULN) for the assay with associated elevation of BNP or other significant cardiac symptoms or findings. A significant elevation of BNP is defined as a $\geq 20\%$ increase over baseline with an absolute value > 100 pg/mL. Subjects who are found at Screening to have baseline troponin-T $>$ ULN or BNP > 100 pg/mL must have a baseline evaluation by a cardiologist during screening to optimize cardioprotective therapy.

After the first 12 cycles of CC-122, in the absence of Grade ≥ 2 adverse events related to CC-122, and as clinically indicated, some clinic visits and assessments may become less frequent as detailed in Section [6.6](#).

6.1.6. 12-Lead Electrocardiogram

TriPLICATE or single standard 12-lead ECGs will be recorded at the visits listed in [Table 3](#) through [Table 5](#). The 12-lead ECGs (12-lead at 25 mm/sec reporting rhythm, ventricular rate, PR-interval, QRS complex, QT interval, and QTc interval) will be performed after the subject has been in the supine position for at least 5 minutes.

TriPLICATE ECGs (3 recordings within 2 ± 1 minute intervals) will be performed at Screening for all subjects. In addition, triplicate ECGs will be collected as follows:

Arm A: Cycle 1 Day 1: 0 and 1.5 hours (± 15 minutes) after CC-122 dosing

Arm B: Cycle 1 Day 1: 0 and 1.5 hours (± 15 minutes) after ibrutinib dosing
Cycle 2 Day 1: 0 and 1.5 hours (± 15 minutes) after CC-122 dosing
Cycle 2 Day 15: 0 and 1.5 hours (± 15 minutes) after CC-122 dosing

Arm C: Cycle 1 Day 1: 0 and 1.5 hours (± 15 minutes) after obinutuzumab dosing
Cycle 1 Day 9 and Cycle 1 Day 23: 0 and 1.5 hours (± 15 minutes) after CC-122 dosing

A single ECG will be performed on all other visits where an ECG is indicated per [Table 3](#) through [Table 5](#) approximately 1.5 hours (± 15 minutes) after dosing.

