6. History of second malignancies with life expectancy of < 2 years or requirement of therapy that would confound study results. This does not include the following:
 - a. Basal cell carcinoma of the skin.
 - b. Squamous cell carcinoma of the skin.
 - c. Carcinoma in situ of the cervix.
 - d. Carcinoma in situ of the breast.
 - e. Carcinoma in situ of the bladder.
 - f. Incidental histologic finding of prostate cancer (TNM stage of T1a or T1b).
7. Known seropositivity for or history of active viral infection with human immunodeficiency virus (HIV), or hepatitis B or C virus (HBV, HCV).
 - a. Hepatitis B screening is mandatory for all patients (HBsAg and anti-HBc). Patients with active hepatitis B disease should not be treated with obinutuzumab. Patients should be referred to a specialist if they are carriers before treatment

starts (see PI or SmPC). Subjects who are positive for anti-HBC and/or anti-HBs but negative for HBsAg and HBV DNA may be treated after consultation with a hepatologist.

8. Any peripheral neuropathy \geq NCI CTCAE Grade 2.
9. Use of systemic corticosteroids in doses greater than prednisone equivalent to 20 mg/day.
10. Medicines with high probability to cause QT prolongation or torsades de pointes.
Subjects on chronic medications in this category may enroll after discussion with the medical monitor if changing these medications are not in the best medical interest of the patient.
11. History of hypersensitivity to IMiDs® (lenalidomide, pomalidomide, thalidomide).
12. Impaired cardiac function or clinically significant cardiac diseases, including any of the following:
 - a. LVEF $<$ 45% as determined by MUGA scan or ECHO.
 - b. Complete left bundle branch, or bifascicular, block.
 - c. Congenital long QT syndrome.
 - d. Persistent or uncontrolled ventricular arrhythmias or atrial fibrillation.
 - e. QTcF $>$ 470 msec on Screening ECG (mean of triplicate recordings).
 - f. Unstable angina pectoris or myocardial infarction \leq 6 months prior to starting CC-122.
 - g. Uncontrolled congestive heart failure or uncontrolled hypertension.
 - h. Troponin-T value >0.4 ng/mL or BNP >300 pg/mL.

Subjects with baseline troponin-T $>$ ULN or BNP >100 pg/mL are eligible but should have cardiologist evaluation prior to enrollment in the trial for baseline assessment and optimization of cardioprotective therapy and after discussion with the sponsor's medical monitor.

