ORR	Objective Response Rate
PBMC	Peripheral blood mononuclear cell
PD	Progressive Disease
PDwH	PD with histologic transformation
PDw/oH	PD without histologic transformation
PET	Positron Emission Tomography
PFS	Progression-Free Survival
PK	Pharmacokinetic
PR	Partial Response
PRL	Partial Response with Lymphocytosis
PT	Preferred Term
PTT	Partial Thromboplastin Time
QD	Daily Dose
QNS	Quantity Not Sufficient
QTc	Corrected QT Interval
QTcB	Bazett Corrected QT Interval
QTcF	Fridericia Corrected QT Interval

Table 1: Abbreviations and Specialist Terms (continued)

Abbreviation or specialist term	Explanation
Rac	Accumulation Ratio
RBC	Red Blood Cell
RNA	Ribonucleic Acid
RP2D	Recommended Phase 2 Dose
RR	R wave to R wave interval
R/R	Relapsed/Refractory
SAE	Serious Adverse Event
SAP	Statistical Analysis Plan
SBP	Systolic Blood Pressure
SD	Stable Disease
SE	Standard Error
SGOT	Serum glutamic oxaloacetic transaminase
SGPT	Serum glutamate pyruvic transaminase
SLL	Small Lymphocytic Lymphoma
SMQ	Standardized MedDRA Queries
SOC	System Organ Class
SPD	Sum of the product of the Perpendicular Diameters for multiple lesions
SRC	Safety Review Committee
StdDev	Standard Deviation
t _{1/2}	Terminal elimination half-life
TEAE	Treatment Emergent Adverse Event
TFR	Tumor Flare Reaction
TLS	Tumor Lysis Syndrome
T _{max}	Time to peak (maximum) drug concentration
TN	Treatment Naïve
TNF	Tumor Necrosis Factor
TSH	Thyroid Stimulating Hormone
Vz/F	Apparent volume of distribution during the terminal phase after extravascular administration
WBC	White Blood Cell
WHO	World Health Organization

Table 1: Abbreviations and Specialist Terms (continued)

Abbreviation or specialist term	Explanation
WHODrug	World Health Organization Drug Dictionary
ZAP 70	Zeta-Chain-Associated Protein Kinase

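### QTc is recorded on timed triplicate ECGs, but the visible SAP tabulates only the reader's overall ECG call, so QTc gets no numeric summary.

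*SAP*

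**What the plan says.** **Collection.** Protocol 6.1.6 lists what each ECG yields: "12-lead at 25 mm/sec reporting rhythm, ventricular rate, PR-interval, QRS complex, QT interval, and QTc interval". Triplicates are "3 recordings within 2 ± 1 minute intervals) will be performed at Screening for all subjects". On-treatment triplicates are timed at 0 and 1.5 hours on one day in Arm A (Cycle 1 Day 1), three in Arm B (Cycle 1 Day 1, Cycle 2 Days 1 and 15) and three in Arm C (Cycle 1 Days 1, 9 and 23). An example is "Cycle 2 Day 15: 0 and 1.5 hours (± 15 minutes) after CC-122 dosing". Other scheduled ECGs in that section are single recordings about 1.5 hours after dosing.

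**Eligibility.** Protocol 7.3 excludes subjects with QTcF above "470 msec on Screening ECG (mean of triplicate recordings"), and congenital long QT. It also restricts "Medicines with high probability to cause QT prolongation or torsades de pointes", but chronic users may enrol after discussion with the medical monitor.

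**Analysis.** Protocol 10.7 covers vital signs, ECG and LVEF in one sentence that asks for cross-tabulations of normal and abnormal values. SAP 11.4 gives the "Shift from baseline to worst post-baseline in the overall ECG interpretation" on three levels (normal, abnormal without clinical significance, abnormal with it) and an ECG listing with unspecified contents. SAP 7.2 also uses only the overall interpretation at baseline. QTc, QTcB and QTcF ("Fridericia Corrected QT Interval") are in the SAP abbreviation list but in no visible analysis section.

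**The concern.** The overall interpretation pools rhythm, conduction and interval findings into a single call, and the worst-post-baseline rule removes timing. A numeric QTc measurement, averaged over triplicates and placed at fixed times around dosing, is thus reduced to whether a reader's summary label changed.

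Safety is the primary objective in every arm, and the preliminary RP2D for Arms B and C rests on an integrated safety assessment. Following the visible SAP, the report would hold no table of how far QTc moved, at what time after dosing, in which arm or at which dose. It could say only how many overall calls worsened.

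**Working it through.** No figure in the plan needs to be reproduced. The check compares the sections and then counts the data affected.

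**Step 1. Three measures, one protocol sentence.** Protocol 10.7 treats all three alike. The SAP does not:

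| Measure | Normal/abnormal shift | Numeric values and change from baseline | Severity grade table |
|---|---|---|---|
| Vital signs (SAP 11.3) | yes | yes | no |
| LVEF (SAP 11.5) | yes | yes | yes |
| ECG (SAP 11.4) | yes | no | no |

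SAP 15, which lists changes to the protocol's statistical section, does not mention ECG. No reason for the difference is given.

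**Step 2. What the shift table can show.**
- A subject called normal at baseline whose QTc rises but whose ECG is still called normal stays on the diagonal.
- A subject already called abnormal without clinical significance stays on the diagonal if QTc rises and the label is kept.
- A subject who moves off the diagonal for a new rhythm finding looks the same as one who moves because of QTc.
- All post-baseline times collapse to the worst call, so the 0 versus 1.5 hour contrast is lost.

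**Step 3. Other places QTc could appear.** The selected TEAEs of interest in SAP 11.1.1 contain no QT grouping. The baseline rule in SAP 17.3 names laboratory tests, efficacy endpoints and vital signs (with a separate rule for biomarkers), but not ECG. Its rule for multiple values at a visit covers laboratory tests and vital signs and takes the latest. Nothing says triplicates are averaged, although eligibility depends on that average.

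**Step 4. Size.** Scheduled triplicate sets per subject = screening + 2 × number of triplicate days; recordings = 3 × sets.
- Arm A: 1 + 2×1 = 3 sets, 9 recordings.
- Arms B and C: 1 + 2×3 = 7 sets, 21 recordings each.
- With the planned numbers in Protocol 7.1 (20, 24, 24): 20×9 + 48×21 = 180 + 1,008 = 1,188.
- With 18 to 36 subjects in each of Arms B and C: 180 + 36×21 = 936 to 180 + 72×21 = 1,692.

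These counts assume that every planned subject completes every set. Later single ECGs come on top.

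**Step 5. Dose labelling.** SAP 5.2.1 summarises Safety subjects under their starting CC-122 dose. Arm A may go from 1.0 to 4.0 mg in 0.5 mg steps every 2 weeks: (4.0 − 1.0)/0.5 = 6 steps, so 4.0 mg can be reached after 12 weeks. Lower cohorts in Arms B and C may also escalate. A table by starting dose would therefore mix doses. In Arm A, the triplicates named in Protocol 6.1.6 fall only at screening and on Cycle 1 Day 1, before any escalation. SAP 5.2.4 already summarises PK samples under the actual dose, so there is a precedent.

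**The case against.** The strongest defence is that the SAP does what the protocol asks. Protocol 10.7 specifies normal/abnormal cross-tabulation for ECG, and SAP 11.4 delivers it on a finer, three-level scale. QTc is not an endpoint, no visible decision rule uses a QTc value after screening, Phase 2 will not proceed, and cohorts of three to six subjects without a concurrent control can support description only. All of this stands. It limits the weight of the point but does not explain why ECG alone was left at the minimum.

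A reader might infer three stronger things that the documents do not support.
- *That QTc is not reported at all.* SAP 5.1 says listings show raw collected data, so individual QTc values may appear in the ECG listing. QTc prolongation recorded as an adverse event would be tabulated by term, grade, relatedness and cohort under SAP 11.1.1, and a qualifying early Grade 3 or higher event could count as a DLT under Protocol 8.2.7. What lacks a table is interval change that is not recorded as an adverse event and does not alter the overall call.
- *That the triplicates exist because of a known QT concern.* Protocol 8.2.9.2.3 gives potential cardiac toxicity in general as the reason for intensified monitoring, and most of the Introduction is redacted. The Cycle 1 Day 1 sets in Arms B and C are timed to ibrutinib and obinutuzumab, not CC-122. The exclusions make QTc relevant but do not establish the motive.
- *That the SAP departs from the protocol.* It does not; the gap begins in Protocol 10.7.

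Parts of the SAP around sections 12 and 13 are redacted, so an ECG-related analysis there cannot be ruled out. Section 11.4 itself reads as complete.

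**Conclusion.** The point holds as a limited gap that should be closed. In the visible SAP, QTc is neither summarised nor analysed numerically, and a change that leaves the reader's call unchanged would reach no ECG table. The volume affected is up to 1,188 scheduled triplicate recordings at planned enrolment (936 to 1,692 over the planned range for Arms B and C), plus later single ECGs. The number actually enrolled before 05 Jul 2018 is not given.

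The conclusion rests on two assumptions: that the redacted SAP text holds no QTc analysis, and that interval values reached the database. Protocol 6.1.6 requires them to be recorded on the ECG but does not say they are entered in the eCRF. No dose, eligibility or stopping rule is called into question.

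**What to change.** 1. In SAP 11.4 add descriptive statistics for QTcF and its change from baseline by scheduled time point, arm and dose cohort, using the mean of triplicates where taken.
2. Add one table of pre-specified categories of maximum post-baseline QTcF and of increase from baseline. The cut-offs are reporting bins for the sponsor to choose, not clinical rules; the documents give none beyond the 470 msec screening limit.
3. Where doses were escalated within subject, report the actual CC-122 dose at the time of the ECG.
4. In SAP 17.3 define the ECG baseline, including whether the 0 hour set on the first dosing day counts as pre-dose, and state the triplicate-averaging rule. The rule needs to cover Protocol 6.6, which calls the ECG from Cycle 13 single yet describes three recordings; that wording should be reconciled.
5. Name QTcF in the ECG listing. Keep the interpretation shift table.

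The cost is a few extra tables, descriptive only in small cohorts. If QTcF was not captured, it has to be derived from QT and heart rate; if neither was entered, the values would first have to be retrieved from site records. No new assessments are needed.
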